Studies of the upper and lower airways of human infants with RSV bronchiolitis are required to definitively understand pathological mechanisms. Studies in infants are difficult to undertake, especially as the child may be clinically unstable and conventional procedures to obtain samples may be too invasive. Infants who require mechanical ventilation for severe RSV bronchiolitis are tracheally intubated, sedated and have indwelling vascular catheters. This allows access to the respiratory tract and enables blood sampling.

In infants naturally infected with RSV, the presence of virus is generally detected in nasopharyngeal aspirate (NPA) samples (5;9). In the UK it is standard clinical practice to perform NPA sampling by direct suction of secretions. However, because this involves the introduction of a suction catheter into the nostril and then to the back of the nose, this procedure may be relatively unpleasant. Sampling by NPA has been found superior to nasal swabs manufactured from natural products (10;11).

Using nasal swabs in young children is rapid and painless and also accurate for RSV diagnosis (12). There is concordance between nasal and nasopharyngeal (NP) swabs for viral testing (13). In a comparison with NPA, nose and throat swabs were more comfortable and have less risk of harm in a clinical setting, but NPA is still recommended in a hospital context (14). Flocked nylon swabs gave higher viral loads than cotton swabs when using qPCRs for detection of human rhinovirus (15).

Viral load may be obtained from these samples by quantitative polymerase chain reaction (qPCR) of infectious samples. This correlates with disease severity in infected infants (4;5). In adults infected experimentally with RSV, the viral load peaks before maximal clinical symptoms (6). It is a major parameter in quantitating the magnitude of infection (7). In assessing the effects of novel therapeutics in experimental infection, the area under the curve (AUC) of viral load is generally the primary end point (8). To determine this, daily samples over the disease course are required. However, there are concerns regarding the accuracy of viral load detection from routine NPA samples as this is dependent of the amount of mucous suctioned at the same time, which varies enormously from patient to patient.

The current methods of sampling described above have a number of limitations:

- Samples are often diluted in saline which can lead to poor sensitivity

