In summary this study will compare the novel methods of NS and BS with the standard technique of nasopharyngeal aspiration (NPA) and routine ETT suction. We shall assess the samples for diagnosis of RSV, viral load and immune responses in the airways of babies with RSV infection. We shall also assess the genetics of babies included in this study, to see if they may be vulnerable to RSV infection.

AIMS

The study involves obtaining nasal samples from babies with suspected RSV infection in the emergency department (ED), as well as those admitted to the paediatric wards and PICU at St. Mary's Hospital, London. This will help us to understand the epidemiology of and the host response to RSV infection in infants both hospitalised and in the community. In addition, we shall take nasal samples from infants attending hospital for outpatient appointments, routine elective surgery and admitted to PICU for non-respiratory diagnoses as controls.

The specific aims are:

1. To study different sampling methods; comparing the established method of NPA and tracheal suction to nasosorption and bronchosorption. We will assess sample volumes, clinical tolerability and virology results: especially viral load.
2. To assess the safety and validity of using bronchosorption to take bronchial MLF samples.
3. To study severity of disease and correlate this with quantitative RSV PCR.
4. To study the incidence of RSV A and B infection, different subtypes of RSV infection.
5. To measure the nasal and bronchial mucosal immune response: in terms of cytokines and chemokines, especially those relating to interferons.

6. To identify if there is a genetic predisposition to severe RSV infection
7. To understand feasibility of these sampling processes in preparation for an interventional study potentially in winter 2017-8.

ENDPOINTS

To compare SAM and nasopharyngeal aspirate (NPA) as sampling methods for measuring RSV viral load.

PRIMARY ENDPOINT: RSV viral load

Virology: How do SAM and NPA compare for RSV viral load determination?

We shall also assess:

- Sensitivity, specificity, quantitation
- Utility for RSV-A vs RSV-B

SECONDARY ENDPOINTS

1. Immune Response: Establishing the use of nasal and bronchial sampling to measure the host immune response to RSV. These techniques could then be applied to the study of drug pharmacokinetics for new therapeutics in future clinical studies.

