2. Epidemiology and virology: This study will assess the number of babies with upper respiratory tract infections (URTI) presenting to St Mary's Hospital ED, the number of babies with confirmed RSV hospitalised on the Paediatrics Ward and also the number admitted to the PICU. The study will assess the relative incidence of RSV A and B and allow us to determine whether RSV subtype is associated with disease severity.
3. Genetics: To establish whether there is a genetic predisposition to severe RSV infection. To carry out genetic analysis by targeted gene sequencing, next generation sequencing or whole genome SNP typing in order to evaluate any genetic deficiencies.
4. Correlation of qPCR with clinical severity

STUDY DESIGN

Type of Study: Pilot study

Duration: To take place in RSV infection season between October and March, starting in October 2015.

Identification of patients: We shall obtain our study groups from patients attending St. Mary's Hospital, London.

Number and types of Subjects:

A total of 5 participant groups (n = 30 in each group)

Details of each group and respiratory sampling procedures are given below:

- *Group 1:* Babies with suspected respiratory tract infection (RTI) in the ED:
 - Nasosorption (NS) in each nostril
 - NPA
- *Group 2:* Babies with diagnosed RSV infection admitted to paediatric wards:
 - NS (2 to 3 times daily, 4-6 hours apart)
 - NPA daily
- *Group 3:* Babies with diagnosed severe RSV infection in PICU requiring mechanical ventilation:
 - NS (2 to 3 times daily, 4-6 hours apart)
 - NPA daily
 - Bronchial aspirate (BA) daily
- *Control Group 1:* Babies without respiratory symptoms, attending routine outpatient appointments or undergoing elective surgical procedures:
 - Nasosorption (NS) only once
- *Control Group 2 :* Babies without RSV infection but requiring mechanical ventilation in PICU:
 - NS (2 to 3 times daily, 4-6 hours apart)
 - NPA daily

Bronchial aspirate (BA) daily

PROCEDURES

Sampling by Absorption:

Nasosorption: SAM strips will be placed inside each of the nostrils for up to 30 seconds. We will place the SAM on the inferior aspect of the inferior turbinate and middle turbinate. There is minimal discomfort in sampling in these areas. This is a well-tolerated, non-invasive procedure without the need for local anaesthetic.

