- ii. **Sample processing** To carry out genetic analysis from DNA/RNA isolated from infants by targeted gene sequencing, next generation sequencing or whole genome SNP typing in order to evaluate any genetic deficiencies.
- iii. **Data Collection** It will be necessary to collect demographic and clinical data from the families in order to define clearly clinical phenotypes. This will include data on age, sex, ethnic groups and clinical details relating to the phenotype. These clinical data will be provided by collaborating clinicians from participating hospitals.

INCLUSION AND EXCLUSION CRITERIA

Group 1 and Group 2

Inclusion Criteria

- Infants aged 2 weeks-24 months
- Presentation to the Emergency Department with any upper respiratory tract infection (URTI) in the RSV season (Oct-March).
OR
- Documented RSV infection, admitted to the paediatric wards at St Mary's Hospital.

Exclusion Criteria

- Any local or systemic factor that would influence the safety of nasal sampling.
- Bilateral indwelling nasal catheters or local nasal pathology preventing access for nasal sampling.
- Bleeding disorders.
- The baby is taking part in another interventional study.
- The parents or guardians not able to sign the informed consent from due to limited English or comprehension despite the use of independent interpreter services.
- Limited life expectancy of the baby,

Group 3

Inclusion criteria

- Hospitalised Infants admitted to the PICU at St. Mary's Hospital, aged 2 weeks-24 months with documented RSV infection (by rapid test and/or PCR).
- Infants of weight >2kg.
- On a conventional ventilator with an Endotracheal Tube (ETT) of ≥ 2.0 mm diameter

Exclusion criteria

- Any local or systemic factor that would influence the safety of nasal sampling.
- Bilateral nasal catheters or local nasal pathology preventing access for nasal sampling.
- The baby is taking part in another interventional study.
- Prematurity - corrected gestational age <36 weeks, weight <2kg
- Significant hypoxia or instability precluding ventilator disconnection
- Transcutaneous oxygen saturation of <95% on 60% oxygen
- Risk of bleeding
- Pneumothorax
- Infants receiving oral corticosteroid therapy at any time in past month
- Parents or guardians not able to sign informed consent from due to limited English or understanding despite the use of independent interpreter services.
- Limited life expectancy or a decision to limit management.

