When sampling is well tolerated there will not be follow up of patients, and the patients will not generally be informed of the result of analyses.

REGULATORY ISSUES

ETHICS APPROVAL

The Chief Investigator has obtained approval from the West Midlands – The Black Country Research Ethics Committee. The study must be submitted for Site Specific Assessment at each participating NHS Trust. The Chief Investigator will require a copy of the Trust R&D approval letter before accepting participants into the study. The study will be conducted in accordance with the recommendations for physicians involved in research on human subjects adopted by the 18th World Medical Assembly, Helsinki 1964 and later revisions.

CONSENT

Consent to enter the study must be sought from each participant's parents or guardians only after a full explanation has been given, an information leaflet offered and time allowed for consideration. Signed consent should be obtained. The right of the parent or guardian to refuse to participate without giving reasons must be respected. After the participant has entered the study the clinician remains free to give alternative treatment to that specified in the protocol at any stage if he/she feels it is in the participant's best interest, but the reasons for doing so should be recorded. In these cases the participants remain within the study for the purposes of follow-up and data analysis. All parents and guardians are free to withdraw at any time from the protocol treatment without giving reasons and without prejudicing further treatment.

CONFIDENTIALITY

The Chief Investigator will preserve the confidentiality of participants taking part in the study and is registered under the Data Protection Act.

INDEMNITY

Imperial College Healthcare NHS Trust London holds negligent harm and non-negligent harm insurance policies which apply to this study. Imperial College Healthcare NHS Trust holds standard NHS Hospital Indemnity and insurance cover with NHS Litigation Authority for NHS Trusts in England, which apply to this study.

SPONSOR

Imperial College Healthcare NHS Trust will act as the main Sponsor for this study. Delegated responsibilities will be assigned to the NHS trusts taking part in this study.

PARTICIPANT REIMBURSMENT

There will be no reimbursement for participating in this study as samples are taken opportunistically.

FUNDING

This study is funded by Pulmocide.

AUDITS

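### Severity is undefined, and with no follow-up or transfer rule, using recruitment setting as severity would misclassify or double-count ED infants who later worsen

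*Combined protocol and SAP*

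**What the plan says.** Under AIMS, item 3 is "To study severity of disease and correlate this with quantitative RSV PCR". SECONDARY ENDPOINTS adds the association of RSV subtype with severity (item 2), genetic predisposition to severe RSV (item 3) and the correlation of qPCR with clinical severity (item 4). None of these gives a severity score, a time at which severity is judged, or a test.

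STUDY DESIGN sets out "A total of 5 participant groups (n = 30 in each group"). Group 1 is "Babies with suspected respiratory tract infection (RTI) in the ED", Group 2 is "Babies with diagnosed RSV infection admitted to paediatric wards", and Group 3 is ventilated RSV infants in PICU. Only Group 3 is called severe.

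Groups 1 and 2 share one inclusion list. Its two routes are joined by OR, and the first is "Presentation to the Emergency Department with any upper respiratory tract infection (URTI) in the RSV season". RSV need not be confirmed on that route. Nothing says whether an infant who moves between settings stays in the first group, is reassigned, or is entered again.

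ASSESSMENT AND FOLLOW-UP states "When sampling is well tolerated there will not be follow up of patients". DATA ANALYSIS nevertheless mentions a follow-up period when setting the data retention time, and CONSENT keeps infants given alternative treatment in the study for follow-up. Neither is defined.

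**The concern.** The care setting is the only ordering of infants that the plan supplies, so an analyst asked to relate viral load or subtype to severity would naturally use it. An infant sampled in ED and ventilated two days later would then sit with the ED infants, or appear in two groups. The background says that in experimentally infected adults "the viral load peaks before maximal clinical symptoms", so an ED sample may well precede the worst of the illness.

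Most missing analysis detail can be supplied later in a fuller SAP. This gap cannot if the later course of ED infants was never collected. At stake are the viral-load and subtype analyses against severity, and any genetic contrast that uses Group 1 as comparator.

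**Working it through.** **Is there a planned route for later course into the data?**
- Groups 2 and 3 are sampled daily in hospital, so worsening during sampling would be seen, although a ward infant later ventilated has no transfer rule either.
- Group 1 has no repeat schedule, and no follow-up is planned when sampling goes well.
- Clinical data to define phenotypes are promised under Blood Genetics Methods, without content or time window.

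So no route is specified for Group 1.

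**Inputs.** The documents give 30 per group, without alpha, power, effect size or SD, so 30 cannot be reproduced. They give no share of ED infants who worsen. Assumptions: f = 5% to 40% of RSV-positive ED infants, and two-sided alpha 0.05. The relevant f depends on the contrast. For ED against hospitalised infants it is the share later admitted. For ED against ventilated infants it is the share later ventilated, which cannot be larger.

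**Attenuation.** Let the mean be E in infants who never worsen and H in those who do. If a share f of the ED group are really of the second kind:

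observed difference = H − [(1 − f)E + fH] = (1 − f)(H − E)

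A true difference of 1.0 log10 would appear as 0.95, 0.90, 0.80 or 0.60 at f = 5%, 10%, 20% or 40%.

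**How many infants.** The count is 30 × r × f, where r is the RSV-positive share of Group 1 (not given). With r = 100% it is 1.5 to 12 infants; with r = 50% it is 0.75 to 6.

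**Power, for scale only.** With 30 against 30, 80% power needs a standardised difference of (1.960 + 0.842) × √(2/30) = 0.72. Power after dilution is Φ(0.723 × (1 − f) × √15 − 1.96):

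| f | observed d | power | n per group for 80% |
|---|---|---|---|
| 0 | 0.72 | 80% | 30 |
| 5% | 0.69 | 76% | 34 |
| 10% | 0.65 | 71% | 38 |
| 20% | 0.58 | 61% | 47 |
| 30% | 0.51 | 50% | 62 |
| 40% | 0.43 | 39% | 84 |

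Allowing for the extra variance of the mixed group lowers these slightly (59% at f = 20%, 37% at 40%).

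**Binary factor such as subtype.** Assume 70% in the severe group against 35% in the other. At f = 20% the second share becomes 0.35 + 0.20 × 0.35 = 0.42. The odds ratio falls from 4.33 to 3.22 and power from 79% to 59%.

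**RSV status.** If half of Group 1 is RSV-positive (assumption), the contrast is 15 against 30. Power at d = 0.72 is then 63% with no misclassification and 45% with f = 20%. Loss of RSV-positive infants alone costs about as much as f = 20% does.

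**Why the direction is open for viral load.** If later-worsening infants have mean load M in their ED sample, and M differs from H:

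observed difference = (1 − f)(H − E) + f(H − M)

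An ED sample nearer the viral peak (M above H) shrinks the difference by more than f; M below H shrinks it by less. E and H may themselves come from different illness days, which can move the contrast either way. Genotype does not change with illness day and infecting subtype hardly does, so the plain mixture is more reasonable there.

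**Double entry** is a separate problem. It puts the same infant on both sides of a contrast and breaks independence. The formula does not describe it.

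**The case against.** The strongest reply is that the protocol never equates severity with recruitment group. It does not call Group 1 mild, say that its infants are sampled only once, or require an ED infant to stay there. That is correct. A reader might infer that severity is fixed at enrolment, but the documents leave it undefined, so the misclassification is conditional on how the analysis is done.

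The follow-up sentence is tied to tolerance of sampling, so it may concern only safety after the procedure, and it does not forbid reading the hospital record. This also stands. But no other section tasks anyone with doing so. The phenotype data have no time window, and the SAE definition is limited to unexpected events.

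Two further inferences do not hold. One is that every severity contrast is biased toward no difference: for viral load, illness day leaves the direction open. The other is that a fixed share of all 30 Group 1 infants is affected: the share applies only to those who are RSV-positive. It is also fair that the genetics text names no Group 1 comparator; that contrast is exposed only if one is used.

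Finally, this is a pilot study, and the primary comparison takes SAM and NPA from the same infant, so it does not depend on severity.

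**Conclusion.** The point holds in conditional form. Severity has no definition, the later course of ED infants has no specified route into the data, and transfers have no rule. If recruitment setting stands in for severity, a share f of misclassified RSV-positive infants removes a fraction f of a two-group difference, which is 5% to 40% over the assumed range. At the low end the loss is minor (80% power becomes 76%); at 20% it is material (61%). These figures rest on assumed f, effect sizes and alpha, and on a plain mixture. For viral load, neither direction nor size is established. Ward against PICU is less exposed, and the primary endpoint is unaffected. It is worth correcting because the information may be unrecoverable if it is not collected.

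**What to change.** - Keep the recruitment group for the comparison of SAM with NPA.
- For the severity analyses, restrict to RSV-positive infants and count each once. Classify by the highest level of care reached in that illness (discharged from ED, ward, ventilated in PICU), read from the hospital record at a fixed point, for example 14 days after the first sample.
- State how an infant who moves between settings is handled, and which sample enters the severity analysis.
- Record day of illness at sampling and account for it in the viral-load analysis. Without this, early ED samples would be compared with samples taken after ventilation began.
- Amend ASSESSMENT AND FOLLOW-UP to allow the record check, with no extra visit or sample, and reconcile it with the undefined follow-up wording in DATA ANALYSIS and CONSENT.

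The cost is one look-up per infant, a few database fields, and a sentence in the protocol and the information leaflet. Admissions to other hospitals would be missed, and the severity groups would no longer be 30 each.
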